Specific Aim 2: In a subset of patients aged 18-25 years, to measure aPWV and FMD_{BA} during normal vs. reduced (via acute ascorbic acid infusion) oxidative stress, and to measure circulating/urine markers of oxidative stress and inflammation before and after 12 months of oral curcumin or placebo.

Hypothesis 3: Oral curcumin therapy will reduce the rate of kidney growth in children and young adults with ADPKD as compared to placebo.

Specific Aim 3: To quantify TKV measured with MRI before and after 12 months of oral curcumin or placebo.

Impact on the field. This study has the potential to establish a **novel, safe, and easy to deliver therapy** for the treatment of arterial dysfunction, and possibly renal cystic disease, in an understudied population of children and young adults with ADPKD.

Research Strategy

Significance

Autosomal Dominant Polycystic Kidney Disease (ADPKD) and Cardiovascular Disease (CVD). ADPKD is the most common lethal genetic kidney disorder ^{1,2}. While the hallmark of ADPKD is the development and continued growth of multiple renal cysts that result in ultimate loss of kidney function ⁴, the leading cause of death among affected patients is cardiovascular in nature ^{1,2}. The proteins encoded by the PKD-1 and -2 genes, polycystin-1 and -2, are expressed in vascular endothelial cells and smooth muscle cells of all major vessels, resulting in extrarenal manifestations of the disease ²³. There are presently very limited treatment options for the prevention of CVD in patients with ADPKD.

ADPKD in Children and Young Adults. Although often considered to be a disease of adults, ADPKD begins in childhood ³ and can in fact be diagnosed *in utero* ²⁴. Even in children with ADPKD, evidence of CV abnormalities begin to manifest, such as elevated blood pressure and increased left ventricular mass index ²⁵⁻²⁷. There are presently very limited treatment options for the prevention of CVD in adults with ADPKD. Thus, childhood/early adulthood may represent a **critical therapeutic window** to prevent future CV complications.

Vascular Function and CVD. As much as 80% of all CVD is associated with dysfunction and disorders of arteries ⁵. Two of the greatest contributors are the development of vascular endothelial dysfunction, most commonly assessed as impaired endothelium-dependent dilation (EDD), and stiffening of the large elastic arteries ⁶, both of which independently predict of future cardiovascular events and mortality ⁷⁻¹⁰.

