Study Modifications to Account for COVID-19 Outbreak. On account of COVID-19 and Institutional policies in place regarding work-related travel, the length of treatment of participants in may be extended due to extenuating circumstances. The end-of-study visit may be delayed due to concerns over air travel, in which case participants will be asked to continue taking the curcumin/placebo, as they have been doing for the past year, and we will reschedule their end-of-study visit at the earliest time point that seems appropriate (hopefully within a couple of months). We will obtain in-person data at this time, but will ask participants to go to our contract laboratory for the clinical labs at the planned 12 month time point if possible. We do not see any additional risk posed to participants by extending their treatment period, as curcumin already has a very favorable safety profile.

Summary of risks associated with curcumin. Based on preliminary studies (see below) and an extensive review of literature, the proposed doses of curcumin are both physiologically relevant and predicted to be well-tolerated by the great majority of study participants. The primary risk associated with curcumin supplementation is the possibility of temporary/transitory gastrointestinal distress (flatulence, constipation, diarrhea, nausea) in a very small percentage of individuals ^{61,65,67}.

Measurements.

Screening Measures. Subjects will undergo a medical history and physical exam, including growth parameters and Tanner staging ⁷⁴⁻⁷⁶, aspartate aminotransferase (AST), alanine aminotransferase (ALT), and a pregnancy test for all female participants of possible childbearing potential (Tanner Stage 2 or higher). Serum creatinine will be measured for determination of eGFR using the CKid Schwartz bedside equation for ages 6-17 ⁵² and the CKD-EPI equation for ages 18-25 ⁵³. A local contracted laboratory (Quest) and medical records will be used for out of state participants. EMLA cream may be used as needed to numb the skin prior to drawing blood.

Measures of Adherence and Safety:

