Adherence. As we expect ~50% of all participants to be from out of state, progress will be reviewed with a monthly phone inquiry of medication supply. Please note, due to the long history and prestige of University of Colorado PKD Center studies, our families have tremendous relationships with our research staff (i.e. investigators and research coordinators). The co-mentor, [name], has successfully employed this approach in previous clinical trials in children/young adults with ADPKD that have included ~50% out of state patients ^{54,56}. We expect the minimal side-effects associated with curcumin to favor adherence. Participants will have powder mailed every 3 months and will also be asked to mail back the bottle for a volume check.

Safety Checks. While adverse events are not anticipated, a safety questionnaire will be administered over the phone monthly. Serum creatinine, ALT and AST will be measured after 1, 6, and 12 months, and for those out of state, will be performed at a local contracted laboratory (Quest). Home pregnancy tests will be required monthly for all girls of possible childbearing potential (\geq Tanner Stage 2). All subjects will be given a digital blood pressure monitor (A&D Medical, UA767) with an appropriately sized cuff and the subject/parent will be instructed in its use. Home blood pressures will be taken monthly and reported during phone safety checks. This approach has been successfully employed previously by the co-mentor, [name] ^{54,56}.

Plasma Curcumin Concentrations will be assessed at baseline and 12 months by liquid chromatography-tandem mass spectrometry (LC-MS/MS) at the University of Rhode Island ⁷⁷. Additionally, curcumin concentrations will be measured by the in red blood cells, the buffy coat, and plasma with the addition of citrate to prevent the degradation of metabolites.

Randomization will be performed by the statistician, using a blocked randomization sequence, with stratification by age group (6-13 or 14-25 yrs).

Outcome Measures. The following measurements will be made at baseline and after 12-months of treatment:

Primary (Functional) Outcomes (Specific Aim 1)

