- Tend to ↓ the progression of TKV (adjusted for height), which can be examined further in a longer-duration, larger sample size, future R01 grant

Power Calculations and Statistical Analysis. Power calculations are based on clinically meaningful differences in the primary outcomes (FMD_{BA} and aPWV), limited published literature using curcumin in a healthy older population⁴⁴, and experience of the applicant regarding the variability of the proposed outcomes^{68,69,79}. A sample size of 27 in each group will have 90% power to detect a mean increase in FMD_{BA} of 1.5%, given a standard deviation of 2.0⁶⁸, with $\alpha = 0.025$, adjusted for two primary endpoints. Akazawa et al.⁴⁴ demonstrated in healthy post-menopausal women a ΔFMD_{BA} of +1.5% with curcumin compared to a decrease in FMD_{BA} of -0.2% in controls. Similarly, a sample size of 27/group will have 90% power to detect a mean decrease of aPWV of 100 cm/sec given a standard deviation of 125⁶⁹ with $\alpha = 0.025$, adjusted for two primary endpoints. To account for a potential dropout of 20%, 34 subjects/group will be enrolled.

A sub-sample size of 10 in each group (of 18-25 year olds) will have 89% power to detect a 50% reduction in ΔFMD_{BA} with ascorbic acid (given $\Delta FMD = +3.0 \pm 1.0\%$ with ascorbic acid in the placebo group⁶⁸), with a two-sided $\alpha = 0.05$. Aim 3 will be considered exploratory, thus power was not calculated.

Differences between groups at baseline will be assessed by an independent t-test, and a linear mixed-effects model will be fit to compare curcumin vs. placebo (independent variable) with respect to change in outcomes at 6 and 12 months (dependent variables), with covariates and potential confounders (including puberty) incorporated into the model. This approach will account for the use of multiple time points and is flexible to missing (at random) data. Although I do not expect different responses based on sex or race/ethnicity, and the study is not powered to assess these factors, stratified analysis will be performed and any trends will be noted and studied in a larger follow-up study. Dropouts will be handled using an intent-to-treat analysis.

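### End-of-study scans delayed by COVID-19 leave TKV change covering unequal intervals, while the analysis text makes no use of actual elapsed time and so does not estimate the growth rate in Hypothesis 3

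*Combined protocol and SAP*

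**What the plan says.** Under Study Modifications to Account for COVID-19 Outbreak, the protocol states that "The end-of-study visit may be delayed due to concerns over air travel". In that case "participants will be asked to continue taking the curcumin/placebo, as they have been doing for the past year", and the visit is rescheduled "at the earliest time point that seems appropriate (hopefully within a couple of months"). That is a hope, and no upper limit is given. The in-person data (vascular tests and MRI) are taken at the late visit. For blood tests, the team "will ask participants to go to our contract laboratory for the clinical labs at the planned 12 month time point if possible".

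The rest of the plan keeps to 12 months. The Outcome Measures section says: "The following measurements will be made at baseline and after 12-months of treatment". Specific Aim 3 is "To quantify TKV measured with MRI before and after 12 months of oral curcumin or placebo", and it serves Hypothesis 3: "Oral curcumin therapy will reduce the rate of kidney growth". The section on MRI measurement adjusts TKV for height and mentions no adjustment for time. Power Calculations and Statistical Analysis specifies a linear mixed-effects model "with respect to change in outcomes at 6 and 12 months (dependent variables"), with covariates left open apart from puberty. Nowhere is there a visit window, a rule for labelling a late visit, a use of actual elapsed time, an annualised TKV change, or a sensitivity analysis for timing.

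**The concern.** A before/after difference equals a yearly rate only when the interval is one year. Once the second scan can slip, two participants whose kidneys grow at the same rate can have different change scores. Hypothesis 3 concerns a rate, so the raw difference no longer matches the stated target. Although Aim 3 is exploratory, the protocol intends any TKV trend to inform the design of a longer trial, and an inflated change would carry forward.

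Among the primary endpoints, the protocol itself notes that aPWV changes across puberty and relies partly on 6-month measurements in local patients to help account for this. Out-of-state participants, about half the sample, have no 6-month vascular visit and are the likeliest to be delayed by air travel.

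The plan's silence also leaves the choice between nominal and actual time open until after the data are seen.

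**Working it through.** **Plan's own figure.** There is none on this point. From the plan I take 27 completers per arm (the power section), a hoped-for delay of about 2 months with no limit, and randomisation in blocks stratified by age group only. Everything else below is assumed: the fraction delayed f, delays k other than 2 months, and kidney growth.

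**1. One participant, linear growth.** Inflation of the raw change = (12 + k)/12 − 1.
- k = 2: 14/12 − 1 = 17%
- k = 6: 18/12 − 1 = 50%

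With compound growth of 3% to 10% a year, the ratio to 12-month growth is 1.17 to 1.18 at 2 months and 1.51 to 1.54 at 6 months, so the choice of growth curve hardly matters.

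**2. Average growth.** Overstatement = f × k/12.
- f = 20%, k = 2: 0.20 × 2/12 = 3.3%
- f = 30%, k = 6: 0.30 × 6/12 = 15%

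**3. Treatment difference.** If 20 of 54 are delayed 6 months, the mean interval is 12 + 20 × 6/54 = 14.2 months. An assumed true effect of 3.0 percentage points a year then becomes about 3.0 × 14.2/12 ≈ 3.5 points on the raw scale. Simulation gave 3.5 raw and 3.0 annualised.

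**4. Balance between arms.** With delay independent of arm, the expected difference in mean interval is zero. Its chance SD is k × √(2f(1 − f)/27).
- f = 20%, k = 2: 2 × √(0.32/27) = 0.22 months
- f = 30%, k = 6: 6 × √(0.42/27) = 0.75 months

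In simulation (27 per arm; growth 6 points a year, between-person SD 5, measurement error SD 3), type I error for raw TKV change under random delay was 0.049 to 0.051. For an unlucky split of 14 v 6 delayed, the spurious difference is 6 × (8 × k/27)/12 points.
- k = 2: 0.3 points
- k = 6: 0.9 points, with simulated type I error 7.1% conditional on that split

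**5. Added variance.** Variance from unequal intervals = g² × f(1 − f) × (k/12)², with growth g = 6 points a year, compared with an assumed SD of TKV change of 5 to 8 points.
- f = 20%, k = 2: 36 × 0.16 × 0.0278 = 0.16, or 0.3% to 0.6% of 64 to 25
- f = 30%, k = 6: 36 × 0.21 × 0.25 = 1.89, or 3% to 8%

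**6. Does annualising work?** Take 6% compound growth scanned at 14 months. The raw change is 1.06^(14/12) − 1 = 7.0%. The ln change is 0.0680, and 0.0680/(14/12) = 0.0583 = ln(1.06). The yearly rate is recovered.

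**The case against.** The plan is silent rather than wrong. It names 6 and 12 months as planned assessments and leaves the covariates open, and a mixed model could take actual time. The TKV target is described as a rate, so an analyst might annualise without being told. That stands as a reading: a reader might infer that late visits are analysed as if they were month 12, but the documents do not say so.

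A reader might also infer that the arms are compared over systematically different durations. The documents do not support that either. The stated cause of delay is travel, the trial is randomised and double-blind, and nothing ties delay to arm. Residence is not a stratification factor, so chance imbalance is possible. It is small for a 2-month delay, and across randomisations the usual standard error allows for it.

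In the scenario that the protocol describes, delays of a couple of months, the effects are small, and the larger figures need longer delays. Aim 3 is exploratory and unpowered, and the protocol concedes that 12 months is probably too short for TKV. It speaks only of a trend to inform a later application and promises no yearly design figure. For FMD, it reports that available data show no change across puberty. All of this limits the size of the problem.

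It does not remove the mismatch for TKV. The only adjustment stated is for height, and a raw change over unequal intervals is not a rate.

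**Conclusion.** The point holds for TKV as a mismatch between the stated analysis and the stated hypothesis. The final scan can be late without limit, and no text brings actual elapsed time into the analysis. One person's raw change is inflated by about 17% at 2 months and 50% at 6 months, and average growth by about 3% to 15% across the two scenarios. These figures rest on roughly linear growth and on assumed numbers delayed, since the documents do not give how many visits were affected or for how long. The consequence is a blurred quantity, a modestly overstated yearly change or effect, some added variance and possible chance imbalance. Systematic bias for or against curcumin does not follow.

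For FMD and aPWV the documents support less: the effect measured is at 12 months or somewhat later, and its sensitivity to timing should be shown. The change is worth making before unblinding.

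**What to change.** Add one paragraph to the analysis section before unblinding.

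- **TKV (exploratory).** Analyse the annualised rate: change in ln(height-adjusted TKV) divided by the actual years between the two MRIs, compared between arms with baseline ln(height-adjusted TKV) as covariate. Report the distribution of intervals by arm.
- **FMD and aPWV.** Keep the planned visit-based mixed model, and say explicitly that a delayed final visit enters as the end-of-study visit. Add a sensitivity analysis restricted to final visits close to month 12, with the window fixed in advance.

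I would not move the primary vascular model to continuous time. Out-of-state participants have a single post-baseline vascular measurement, so the model would need an assumed time course for the treatment effect. A linear one sits badly with the protocol's preliminary data in older adults, where FMD had already improved at 3 months.

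The cost is small: no new participants or measurements, only visit and scan dates. The one added assumption is roughly constant proportional kidney growth over the interval between scans.

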
 Aged 6-25 years ADPKD diagnosis based on bilateral renal cysts + positive family history⁵¹ Normal renal function with an estimated glomerular filtration rate (eGFR) >80 mL/min/1.73 m² (using CKid Schwartz bedside equation for ages 6-17⁵² and the CKD-EPI equation for ages 18-25⁵³) Ability to provide informed consent or assent 	
 Currently taking a curcumin supplement Current smokers or history of smoking in the past 12 months Marijuana use within 2 weeks prior to FMD_{BA} and aPWV testing Antioxidant and/or omega-3 fatty acid use within the past 4 weeks prior to FMD_{BA} and aPWV testing and for the duration of the study Alcohol dependence or abuse History of hospitalization within the last 3 months Active infection or antibiotic therapy Pregnancy, lactation, or unwillingness to use adequate birth control Body-mass index ≥95th percentile in ages 6-17 or >40 kg/m² in ages 18-25 (vascular measurements can be inaccurate if severely obese) Inability to cooperate with/clinical contraindication for MRI including severe claustrophobia, implants, devices, or non-removable body piercings

Experimental Design (Figure 1). A 1-year randomized, placebo-controlled, double-blind design study with curcumin will be conducted. Subjects will undergo telephone and laboratory screening for inclusion/exclusion criteria and will then be randomly assigned to either curcumin or placebo. Members of the investigative team involved in the acquisition and analysis of data will be blinded to the treatment status. Vascular function measurements will be made under supine, overnight fasted (water only) conditions before and after 1-year of the intervention, and at 6-months in local patients to reduce variability over time and better establish timeline of change. Females who are post-pubertal will be scheduled during the first week of their menstrual cycle, when estrogen and progesterone are lowest, minimizing the impact of hormonal variations on vascular function⁵⁷.

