Brachial Artery FMD and Endothelium-Independent Dilatation. FMD_{BA} will be determined using high-resolution ultrasonography (Toshiba Xario 200) as described originally by Celermajer et al. ⁷⁸ and used recently by the applicant ^{68,79,80}. FMD_{BA} is a widely used, non-invasive method inducing reactive hyperemia to assess endothelium-dependent dilation. It is validated in children ^{78,81} and is mainly dependent upon NO production ^{82,83}. Brachial artery endothelium-independent dilation will be determined in the sub-group of participants aged 18-25 yrs by measuring brachial artery dilation for 10 minutes after administration of sublingual nitroglycerin (0.4 mg) ^{67,84,85}. This assessment is key to the interpretation that any improvements in dilation are indeed dependent upon endothelial production of NO rather than improved smooth muscle relaxation to NO ⁸⁶. The use of nitroglycerin is currently safely employed in an NIH-funded, IRB-approved protocol in adults with ADPKD at the University of Colorado Denver. A commercially available software package (Vascular Analysis Tools 5.8.1, Medical Imaging Applications) will be used to acquire and analyze ECG-gated brachial artery diameters. Doppler blood flow velocity will be obtained for estimation of shear rate, which will be entered as a covariate if indicated ⁸⁷⁻⁸⁹.

Aortic Pulse-Wave Velocity. aPWV will be determined as described in detail previously by applicant ^{69,90} and validated in children ^{71,91}. Briefly, a transcutaneous custom tonometer (Noninvasive Hemodynamics

Workstation, Cardiovascular Engineering Inc.) will be positioned at the carotid and femoral arteries to non-invasively assess aPWV, as distance/time between the foot of the arterial waveforms⁹². As a secondary index of arterial stiffness, ultrasound imaging of the carotid artery will also be performed for calculation of carotid artery compliance and the β -stiffness index (in conjunction with tonometry), as described previously^{96,97}. The images will also be assessed for measurement of carotid artery intimal-medial thickness (IMT), which is used in the calculation of carotid artery compliance and the β -stiffness index.

Outcomes for Specific Aims 2 (Only in the sub-group aged 18-25 years (except for urinary markers))

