b) Data Safety Monitoring Plan. A data safety monitoring board (DSMB) including clinicians (a nephrologist and pediatrician) and a statistician (independent of the study investigators but part of the faculty at the University of Colorado, School of Medicine) will be formed to assess potential adverse events. These data will be prepared by the DSMB statistician, ensuring the study statistician remains blinded until the final analysis. The DSMB will meet annually to review the protocol and will follow the guidelines established by the NIH National Center for Research Resources which include: a) monitoring the progress of the protocol (e.g., reviewing subject recruitment, attrition and minority involvement) and the safety of research participants (e.g., reviewing unblinded data for safety); b) assuring compliance with requirements regarding the reporting of adverse events; c) assuring that any action that results in the temporary or permanent suspension of the protocol is reported to all the appropriate monitoring bodies (i.e., IRB, NIH, FDA, etc.); and d) assuring data accuracy and protocol compliance.

c) Reporting of Side Effects. Subjects will be instructed to report side effects to the investigator and their nephrologist, if not part of the investigative team. Any serious adverse events will be reported to the Colorado Multiple IRB, Verdure Sciences, and the FDA, in accordance with the guidelines of each of these groups. Participants who drop out of the study will be handled using an intent-to-treat analysis.

d) Exit Criteria. The primary exit criteria will include completion of the study, patient request, IRB or DSMB request, or other rationale as determined by the principal investigator or mentors. Other exit criteria are listed below. The number of subjects exiting the study and the reasons for exit will be carefully documented.

Patient Stopping Criteria:

- Withdrawal of informed consent (subject's decision to withdraw for any reason)
- Any clinical adverse event (AE), laboratory abnormality or intercurrent illness which, in the opinion of the investigator, indicates that continued participation in the study is not in the best interest of the subject
- Pregnancy
- Loss of ability to freely provide consent through imprisonment or involuntary incarceration for treatment of either a psychiatric or physical (e.g., infectious disease) illness
- Use of an investigational therapy or device other than study medication

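### Does giving randomisation to an unnamed statistician break the promise that the study statistician stays blinded?

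*Combined protocol and SAP*

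**What the plan says.** The combined protocol and SAP mentions a statistician in two places.

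- **Randomization paragraph (Approach, after the adherence and safety measures):** "Randomization will be performed by the statistician, using a blocked randomization sequence", "with stratification by age group (6-13 or 14-25 yrs". The role is not qualified. Block size, list custody and a key-release step are not described.
- **Data Safety Monitoring Plan (Human Subjects, section 5b):** the DSMB includes "a statistician (independent of the study investigators but part of the faculty at the University of Colorado, School of Medicine". On the data the board reviews: "These data will be prepared by the DSMB statistician, ensuring the study statistician remains blinded until the final analysis".

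The Experimental Design paragraph adds a general commitment: "Members of the investigative team involved in the acquisition and analysis of data will be blinded to the treatment status". The section on MRI measurement of TKV separately blinds the radiologist, the technicians and the investigator who calculates kidney volume.

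Two analysis choices are left partly open. The mixed model in Power Calculations and Statistical Analysis is to be fitted "with covariates and potential confounders (including puberty) incorporated into the model", and puberty is the only covariate named there. For brachial artery FMD, shear rate is a variable "which will be entered as a covariate if indicated".

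The COVID-19 section shows that the allocation list already exists in this version: "participants will be asked to continue taking the curcumin/placebo, as they have been doing for the past year".

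**The concern.** The DSMB statistician appears only in the safety monitoring section and only for safety data. A reader who meets an unqualified statistician in the methods will therefore think of the trial's own. On that reading the plan asks one person both to generate the blocked list and to remain blinded. The separate data route through the DSMB statistician would then protect nothing, since the study statistician would already know the allocation.

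What would be at stake is the integrity of the remaining modelling choices. Someone who knows the arms could, even without intent, settle whether shear rate is needed, or which confounders to add, in the direction that flatters curcumin. Someone who sees only masked codes cannot steer in a chosen direction. Blinding of participants and of those who acquire and read the outcomes is not in doubt.

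**Working it through.** **1. Do the statements conflict?** Set side by side, they are:

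| Statement | Section | What it fixes |
|---|---|---|
| A statistician randomises | Randomization | The task; the person is not identified |
| The study statistician is blinded until the final analysis | Data Safety Monitoring Plan | The result for that person |
| Those who acquire and analyse data are blinded | Experimental Design | The result for the team |

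At least two arrangements satisfy all three rows. Either someone other than the study statistician generates the list, or the study statistician generates it under masked codes while another person holds the link to curcumin and placebo. Only one arrangement breaks them: the study statistician generates an unmasked list. The plan never describes that one, and its second and third rows rule it out. A sponsor who follows the whole document keeps the blind.

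**2. Does list custody control the feared harm?** The harm is selecting covariates with the arms known. The plan's promise covers the period up to the final analysis. No section promises masked codes during that analysis, or requires the covariate set to be fixed before the key is released. So:

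- with ideal custody and open covariates, the arms may still be known when the covariates are chosen;
- with any custody and fixed covariates, nothing is left to steer.

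The harm follows the open covariates, not the list.

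**3. Does knowing the arms change the rate of wrong conclusions?** The inputs from Power Calculations and Statistical Analysis are 27 per arm, FMD SD 2.0 and planned difference 1.5 percentage points, with alpha 0.025 for each of two primary endpoints. The following are assumed and not in the documents: no true effect; the SD taken as the SD of change; puberty always in the model; four candidate FMD models (baseline in or out, shear rate in or out); baseline to follow-up correlation 0.3, 0.5 or 0.7; covariate loading 0.1, 0.3 or 0.5. Compare two analysts who both hunt through the models:

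- Arms known: take the largest t in favour of curcumin.
- Arms masked: take the smallest two-sided p, then unmask.

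If any model passes the critical value in favour of curcumin, the first analyst claims success. The second picks the model with the strongest two-sided evidence. That model points the same way unless another model on the same data is even more significant in the opposite direction, which nested adjustments of one randomised comparison almost never produce. The two rates must therefore nearly coincide.

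Simulation agrees. With 2,500 null trials in each of nine settings, false claims favouring curcumin ran from 1.7% to 4.2% under both rules. One setting differed, at 4.16% against 4.12%, which is 104 against 103 trials. A separate run gave identical rates in every setting, between 1.7% and 3.1%. The nominal one-sided rate is 0.025/2 = 1.25%. The excess over it comes from hunting through open models, and masking does not remove it.

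**4. What does knowing the arms change?** It changes the average estimate under the null. Always choosing the most favourable of the four models shifts FMD by about 0.12 to 0.20 points:

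- 0.12 / 1.5 = 8% of the planned difference
- 0.20 / 1.5 = 13%

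Under masked codes the mean shift is zero within simulation error. But the figure depends on the assumed menu. Allowing three more optional covariates (correlation 0.5, loading 0.3) raised it from about 0.18 to about 0.39 points, and 0.39 / 1.5 = 26%. The documents give no menu, so no size can be attached to the concern. These simulations also use a single change score, not the planned mixed model with 6- and 12-month data.

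**The case for a change.** The strongest case for a change is that the plan itself treats the study statistician's blindness as worth protecting, builds a separate data route for it, and then leaves open whether that person made the list. One sentence would settle the matter at no cost to sample size, visits or data. Because analysis is scheduled for months 54 to 60 (Study Time Line), custody could still be documented and the covariates fixed in time. Knowing the arms also gives selection a direction, which masked codes do not.

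Part of this stands. The omission is real: nobody is named as list generator or key holder. The plan also does not prove that the blind was kept, and the trial file should be able to show who held the list. But this concerns documentation of conduct. If the study statistician in fact worked from an unmasked list, that would depart from the plan as written, and moving custody now could not restore what that person already knows. Giving the list to the DSMB statistician would also hand an operational task to someone the plan sets apart as independent of the investigators. The point about direction is correct for the mean estimate, but it argues for fixing covariates, which is a separate matter.

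**Conclusion.** The concern does not call for a change. The plan leaves a role unnamed, and the rest of the document constrains how that role may be filled: the study statistician, and everyone who acquires or analyses data, is to be blinded. Ordinary trial practice (another person generating the list, or masked codes with a separate key holder) meets every statement.

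No sample size, power, alpha or estimate in the plan depends on this point. In the null simulations, knowing the arms left the rate of false claims favouring curcumin essentially unchanged. It does shift the mean estimate, but by an amount set by a covariate menu that the documents do not supply, so no magnitude should be quoted.

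This rests on two assumptions: that the sponsor carries out the blinding commitments as written, and that the wording does not conceal an unmasked list in the study statistician's hands. Nothing in the documents indicates that it does.
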